#### 3.1.10. HEPATIC FUNCTION

- Total bilirubin must be  $\leq 1.5$  times the upper limit of normal (ULN)
  - SGPT (ALT) must be  $\leq 3.0$  times ULN
- 3.1.11. RENAL FUNCTION: Serum creatinine  $\leq$  ULN or creatinine clearance  $>60$  ml/min/1.73 m^2
- 3.1.12. Serum triglyceride level  $\leq 300$  mg/dL and serum cholesterol level  $\leq 300$  mg/dL (Patient may be on lipid-lowering medicine)
- 3.1.13. CARDIAC FUNCTION:
- 3.1.13.1. Normal ejection fraction by ECHO or cardiac MRI  $>55\%$
- 3.1.13.2. QTcF  $\leq 450$ ms
- 3.1.14. Fertile men and women of childbearing potential must agree to use an effective method of birth control.

Female patients of child bearing potential must be willing to use 2 forms of contraception (per institutional standards) from the time of screening until 4 weeks after discontinuing the study (1 highly effective and 1 barrier method, see below). They must not be breastfeeding and must have negative pregnancy test prior to start of dosing.

For a female patient to be considered as of not child bearing potential, she should fulfil one of the following:

- Post menopausal women, defined as either women aged more than 50 years and have amenorrhea for at least 12 months following cessation of all exogenous hormonal treatments, or, women under 50 years who have amenorrhea for at least 12 months following cessation of exogenous hormonal treatments, and have serum follicle-stimulating hormone (FSH) and luteinizing hormone (LH) levels in the postmenopausal range for the institution.

OR

- Have documentation of irreversible surgical sterilization by hysterectomy, bilateral oophorectomy or bilateral salpingectomy (but not tubal ligation)
- Have medically confirmed, irreversible premature ovarian failure.

Highly effective methods of contraception are:

- Use of medroxyprogesterone acetate depot injection (Depo-proveraTM). (Please note: use of any other oral, injected, or implanted hormonal methods of contraception cannot be considered highly

effective as it is currently unknown whether selumetinib/sirolimus may reduce their effectiveness)

- Placement of a copper-banded intrauterine device (IUD) or intrauterine system (IUS)
- True abstinence
- Bilateral tubal ligation
- Vasectomized partner

Barrier methods include:

- Condom
- Occlusive cap (e.g. diaphragm or cervical/vault caps) with spermicide

Male patients should either be surgically sterile or willing to use an effective barrier method of contraception during the study and for 16 weeks following the last dose of study treatment if sexually active with a female of child bearing potential. If not done, storage of sperm prior to receiving study treatment will be advised to male patients with a desire to have children.

3.1.15. Patients with central nervous system disease are eligible for enrollment if they have received prior radiotherapy or surgery to sites of CNS metastatic disease and are without evidence of clinical progression or stable disease at 4 weeks.

### **3.2. Exclusion Criteria**

3.2.1. Patients receiving other anti-cancer agents are not eligible.

3.2.2. Patients who cannot swallow whole pills.

3.2.3. Patients receiving chronic, systemic treatment with corticosteroids or another immunosuppressive agent (for example cyclosporine). Topical or inhaled corticosteroids are allowed.

3.2.4. Patients should not receive immunizations with attenuated live vaccines within four weeks of study entry or during study period.

3.2.5. Any recent major surgery within a minimum of 4 weeks, with the exception of surgical placement for vascular access, or minor surgery (excluding tumor biopsies) within 14 days.

3.2.6. Patients who any known severe and/or uncontrolled medical conditions or other conditions that could affect their participation in the study such as:

- Severely impaired lung function defined as spirometry and DLCO that is 50% of the normal predicted value corrected for hemoglobin and alveolar volume and/or O2 saturation that is 88% or less at rest on room air. For patients who do NOT have respiratory symptoms (e.g. dyspnea at rest, known requirement for supplemental oxygen), pulmonary function test is not required.
  - Cardiac conditions as follows:
    - Uncontrolled hypertension (blood pressure  $\geq$ 150/95 mmHg despite medical therapy.
    - Acute coronary syndrome within 6 months prior to starting treatment
    - Uncontrolled angina despite medical therapy
    - Symptomatic heart failure NYHA Class II-IV prior or current cardiomyopathy, or severe valvular disease
    - Prior or current cardiomyopathy
  - Uncontrolled Type 1 or 2 diabetes as defined by fasting serum glucose  $>1.5 \times$  ULN
  - Uncontrolled infection
  - Pre-existing renal disease including glomerulonephritis, nephritic syndrome, Fanconi Syndrome, or renal tubular acidosis.
  - Current refractory nausea and vomiting, malabsorption syndrome, disease significantly affecting gastrointestinal function, resection of small bowel, symptomatic inflammatory bowel disease, or ulcerative colitis, or partial or complete bowel obstruction.
  - Ophthalmological conditions as follows:
    - Current or past history of retinal pigment epithelial detachment (RPED)/central serous retinopathy (CSR) or retinal vein occlusion
    - Intraocular pressure (IOP)  $> 21$  mmHg or uncontrolled glaucoma
- 3.2.7. Supplementation with vitamin E greater than 100% of the daily recommended dose.
- 3.2.8. Hypersensitivity to active or inactive excipients of rapamycins (sirolimus, temsirolimus or everolimus) or selumetinib or drugs with similar chemical structures or class to sirolimus or selumetinib.
- 3.2.9. Patients unwilling or unable to comply with the protocol.

- 3.2.10. Seville orange, star fruit, grapefruit and their juices, and St. John's Wort use are not allowed while on study.
- 3.2.11. Exposure to strong or moderate inhibitors or inducers of CYP3A4/5, Pgp (MDR1) and BCRP if taken within the stated washout periods before the first dose of study treatment (Appendix II).
- 3.2.12. Exposure to specific substrates of drug transporters OATP1B1, OATP1B3, MATE1 and MATE2K within the appropriate washout periods (a minimum of 5 x reported elimination half-life) before the first dose of study treatment (Appendix II)

### **3.3. Inclusion of Children, Women and Minorities**

Men, women, children (as applicable) and members of all ethnic and racial groups are eligible for this trial.

Subjects of both genders and from all racial and ethnic groups are eligible for this trial if they meet the eligibility criteria outlined in Section 3.1. No groups are being excluded from participation in the trial. Approximately 50% of MPNST develop in individuals with NF1, and we expect that approximately 50% of individuals enrolled will have NF1 associated MPNST and 50% will have sporadic MPNST.

The treatment approach to MPNST is similar for children and adults. Approved adult and adolescent drug dosing was determined to be equivalent in approximately 95% of all products with an adolescent indication studied under the FDA amendments act of 2007 [64]. Whereas sporadic MPNST are typically diagnosed in late adulthood, MPNST diagnosis peaks at a younger age in patients with NF1, generally in early adulthood (20-50 years) with 10-20% of cases reported at even younger ages (1-19 years) [12, 13]. Thus, treating patients  $\geq 12$  years of age will allow for the majority of patients with MPNST without affecting safety and dosing per FDA findings.

### **3.4. Human Subjects Protection**

#### **3.4.1. Risks/Benefits Analysis**

The primary risk to patients participating in this research study is from toxicity of the combination of selumetinib and sirolimus. The primary objective of this trial is to determine the clinical response rate in patients with refractory MPNST. Safety and tolerability will be closely monitored. Patients will thus be treated with therapeutic intent and response to the therapy will be closely monitored. Treatment options for these patients are very limited, as most patients will have received prior cytotoxic chemotherapy, which is often considered first line treatment by many oncologists for unresectable high-grade MPNSTs. The protocol provides for detailed and careful monitoring of all patients to assess for toxicity and response to treatment. Patients will be treated with therapeutic intent and response to the therapy will be closely monitored. The potential benefit from this therapy is disease stabilization, tumor shrinkage, and decrease tumor related

symptoms. Therefore, this protocol involves greater than minimal risk to subjects, but presents the potential for direct benefit to individual subjects. For patients who cannot provide informed consent by themselves, but have a durable power of attorney (DPA) this legal representative will be able to provide informed consent for this study.

The medical, hospital, and research records associated with this study are considered confidential. Members of the treating team and designated research study assistants will have access to the records as required to administer treatment and comply with the protocol. Neither the name nor other identifying information for an individual will be used in the report or publication concerning this study. Patient records may be inspected by auditing agencies including the DoD, FDA, and Drug companies that make selumetinib and sirolimus.

### 3.4.2. Informed Consent

The investigational nature and research objectives of this trial, the procedures and treatments involved and their attendant risks and discomforts and benefits, and potential alternative therapies will be carefully explained to the patient or the patient's parents or guardian if the patient is a child, and a signed informed consent and assent document will be obtained according to institutional guidelines prior to entry onto the study. Consent will be obtained by the PI or an associate investigator on this trial. This must be done according to the guidelines provided in the Declaration of Helsinki, ICH E6 Guideline for Good Clinical Practice (GCP), and requirements of Title 21 CFR 50.20 through 50.27. The patient must be made aware and agree that personal information may be scrutinized during audit by competent authorities and properly authorized persons. However, personal information will be treated as strictly confidential and will not be publicly available.

## 4. REGISTRATION PROCEDURES

### 4.1. General Guidelines

After obtaining Informed Consent, eligible patients will be enrolled on this trial. Subjects will be registered by local sites through an electronic database, and will be issued a subject unique identifying numbers for eligible participants. An investigator is required to prepare and maintain adequate and accurate case histories designed to record all observations and other data pertinent to the investigation on each subject treated with the investigational product in the study or registered to the study. SARC may request faxed copies of selected source documents with PHI redacted for verification of records, accuracy of electronic submissions and review of data.

While all study evaluations must be performed by the Investigator as described in Section 10, Study Evaluations and Study Calendar, only data related to the primary and secondary endpoints, as well as safety data, will be captured in the eCRFs.

### 4.2. Registration Process

This study uses a web based data entry system for data submission. All subject registrations and Case Report Forms (CRFs) will be submitted electronically via the study web site. All subjects must be registered on the study website prior to start of treatment. Data Managers and other authorized users will be provided with a unique user identification number and password to access the site. All study case report forms may be accessed online through the study website. In case there are problems accessing the website, please contact the SARC office directly at: [contact], [contact].

## 5. TREATMENT PLAN

### 5.1. Agent Administration

Treatment Schedule		
Selumetinib (mg)	Sirolimus (mg)	
PO BID continuous	Cycle 1 Day 1 loading dose	Maintenance PO once daily continuous
50	12	4
1 cycle = 28 days		

#### 5.1.1. Selumetinib

Selumetinib will be supplied in 10mg and 25mg capsules. Dosing will be orally 50mg twice daily continuously. Patients should be instructed to take selumetinib on an empty stomach (either 1 hour before or 2 hours after meals) with water only. If a patient misses a dose, the dose may be taken within 4 hours of missed dose, otherwise wait until the next dose. If a patient vomits after a dose, it will not be repeated.

The capsules cannot be crushed and have to be swallowed whole. Patients will keep a diary (see operations manual) to document the intake of each dose of selumetinib and potential side effects. The patient diary review and pill count will be done prior to each cycle.

#### 5.1.2. Sirolimus

Sirolimus will be purchased commercially (2mg tablets) and administered once daily. On cycle 1 on day 1, a loading dose of sirolimus will be given orally x 1. Subsequent doses of sirolimus will be 4mg given orally once daily continuously with no breaks in between cycles. Sirolimus should be taken around the same time as the morning dose of selumetinib. Sirolimus should be taken at approximately the same time every day. If a patient misses a dose, the dose may be taken within 4 hours of missed dose. Otherwise, patient must wait until the next day's dose. If a patient vomits after a dose of sirolimus it will not be repeated. Tablets must be swallowed whole. All doses prescribed and dispensed to the patient and all dose changes during the study will be recorded in the patient diary.

One cycle of therapy is 28 days.

### 5.2. Criteria to start subsequent cycles

(Refer to section 6 for dose modifications)

A cycle may be repeated every 28 days if the patient has at least stable disease, has again met the ANC, platelet, hepatic, and renal function defined in Section 3.1, and has not met one of the off protocol therapy or off study criteria in Section 5.6 and 5.8. Up to 21 days (to day 49) will be allowed between cycles for recovery without modifying drugs on subsequent cycles if toxicity did not meet criteria requiring dose modification.

### 5.3. Duration of treatment

Patients may continue therapy as long as they achieve a minimum response of stable disease and do not experience excessive toxicity.

### 5.4. General Concomitant Medication and Supportive Care Guidelines

#### 5.4.1. Concurrent Therapy

- Concurrent cancer therapy including chemotherapy, radiation therapy, immunotherapy or biologic therapy may NOT be administered to patients while on this study. If these treatments are administered, the patient will be removed from protocol therapy.
- No other investigational agents may be given while the patient is on study.

#### 5.4.2. Concomitant Medications

- Doses of vitamin E greater than 100% of daily recommended doses are contraindicated.
- Throughout the study, patients should be instructed to avoid changes to or the addition of concomitant medications, in particular any that may affect the metabolism of selumetinib and sirolimus, unless considered clinically indicated.
- While a patient may not enter a study arm if they have taken within the stated washout periods prior to study start any of the CYP450 isoenzyme inhibitors or inducers detailed in exclusion criteria and in Appendix II, it could be possible to allow their short-term administration during the study if clinically indicated and unavoidable.

#### 5.4.3. Supportive care

Appropriate antibiotics, blood products, anti-emetics, fluids, electrolytes, and general supportive care are to be used as necessary.

#### 5.4.4. Skin and sunlight protection

Recommendations to start on day one of treatment with selumetinib and sirolimus and to continue throughout treatment and 3 months post treatment.

- Use skin moisturizer (thick, alcohol free) at bedtime
- Avoid excessive exposure to sunlight
- Use sunglasses and sunscreen (PABA-free, SPF  $\geq 15$ ; UVA and UVB protection) as needed
- Use of topical retinoids or benzoyl peroxide is not recommended

#### 5.4.5. Management of Rash

Early identification and intervention is critical for optimal management of rash. Patients who develop Grade 1 changes, consider anti-histaminergic drugs, mild/moderate topical steroid and/or topical antibiotic. For Grade 2 changes, consider anti-histaminergic drugs, a moderate strength topical steroid and consider oral antibiotics.

For Grade  $\geq 3$  rash, interrupt selumetinib/sirolimus. Apply moderate strength topical steroid and consider an oral antibiotic. If an infection is suspected, consider other broad spectrum antibiotic coverage. If rash has improved to a Grade 2 or less, restart selumetinib/sirolimus at reduced dose.

Examples of treatments are:

- Topical of moderate strength: triamcinolone, desonide, aclometasone
- Oral antihistamines: loratidine, cetirizine, fexofenadine, diphenhydramine, hydroxyzine

- Topical antibiotics: clindamycin, erythromycin, metronidazole, silver sulphadiazine
- Oral antibiotics: doxycycline, minocycline, oxytetracycline

#### 5.4.6. Management of stomatitis/oral mucositis/mouth ulcers

For mild toxicity (Grade 1), use conservative measures such as non-alcoholic mouth wash or salt water (0.9%) mouth wash several times immediately after drug administration (1 to 3 hours) and during the day as required until resolution. For more severe toxicity (Grade 2 or 3), the suggested treatments are topical analgesic mouth treatments (i.e. local anesthetics such as benzocaine, butyl aminobenzoate, tetracaine hydrochloride, menthol, or phenolic compounds) with or without topical corticosteroids such as triamcinolone oral paste 0.1% (e.g. Kenalog in Orabase®) or alcohol-free 0.5 to 2mg/5mL dexamethasone oral solution (i.e. for example Dexsol® or PMS dexamethasone 0.5mg/5mL elixir). The mouth rinse will be self-administered at a daily dose of 10mL per day. Most importantly, patients must be instructed to swish and expectorate the mouth rinse to avoid systemic exposure to dexamethasone. Agents containing hydrogen peroxide, iodine, and thyme derivatives may worsen mouth ulcers. It is preferable to avoid these agents. For Grade  $\geq 3$  stomatitis/oral mucositis/mouth ulcers, systemic pain killers are indicated.

#### 5.4.7. Management of diarrhea

Patients should be aware diarrhea can occur with selumetinib/sirolimus treatment. Patients should be given loperamide (in accordance with local practice) to take home with them and advised to start after first episode of unformed stool. Patients should be given dietary advice in case of diarrhea (e.g. BRAT [bananas, rice, apple sauce, toast, plain past] diet; readily digestible food, avoidance of lactose-containing products, fried, fatty or spicy food) and increase fluid intake (8-10 glasses of clear fluid daily, including water and fluids containing salt and sugar such as sports drinks and clear broth).

For uncomplicated Grade 1 or 2 diarrhea:

- Patients should immediately start loperamide after the first episode of diarrhea (4mg initially) and continue (2mg every 4 hours or after each unformed stool) until they have been free for at least 12 hours.
- If after 12 hours of loperamide treatment, the diarrhea is not improving, can increase to high dose loperamide (2mg every 2 hours or 4mg every 4 hours) and continue to take loperamide until they have been free from diarrhea for at least 12 hours. Additional treatment may be considered according to local practice.

**\*\*NOTE:** Should NOT exceed 16mg loperamide (i.e. 8 capsules/tablets) over a 24 hour period

For persistent (>24hours) Grade 1 or 2 diarrhea despite loperamide at high dose, the following should be considered:

- Rehydration and electrolyte replacement as appropriate
- Infectious causes and etiologies such as clostridium difficile or viral enteritis
- Antibiotics if appropriate particularly if patient is neutropenic or has fever
- Discontinuation of loperamide and start of octerotide (sandostatin)
- Addition of other second line anti-diarrheal agents according to local practice
- Hospitalization

For any Grade uncontrolled or complicated diarrhea or Grade 3-4 diarrhea, consider:

- Hospitalization
- Intravenous fluids, electrolytes, and antibiotics if needed
- Start octreotide (sandostatin)

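### Section 5.4.7: both high-dose loperamide options total 24 mg in 24 hours against the section's own 16 mg limit, and the next escalation step is worded ambiguously

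*Combined protocol and SAP*

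**What the plan says.** Everything relevant is in section 5.4.7 of the protocol; no other section gives a loperamide schedule. Patients receive loperamide to take home. For uncomplicated Grade 1 or 2 diarrhea the section sets out four elements:

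- **Standard dosing.** "4mg initially) and continue (2mg every 4 hours or after each unformed stool) until they have been free for at least 12 hours".
- **Step-up.** The condition is "If after 12 hours of loperamide treatment, the diarrhea is not improving". The patient then "can increase to high dose loperamide (2mg every 2 hours or 4mg every 4 hours) and continue to take loperamide". The end point is a symptom-free interval, not a number of doses: "continue to take loperamide until they have been free from diarrhea for at least 12 hours".
- **Limit.** A note directly below these two bullets reads "Should NOT exceed 16mg loperamide (i.e. 8 capsules/tablets) over a 24 hour period".
- **Next step.** "For persistent (>24hours) Grade 1 or 2 diarrhea despite loperamide at high dose, the following should be considered". The measures listed include rehydration, an infectious work-up, a switch to octreotide and hospitalization.

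A separate step covers Grade 3-4 diarrhea, and diarrhea of any grade that is uncontrolled or complicated. It has no time trigger and no loperamide schedule.

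**The concern.** A dosing interval with an open-ended duration and a daily maximum should fit together, or the text should say which governs. Here the interval implies a daily total above the maximum. A patient who keeps to the interval passes the limit. A patient who keeps to the limit runs out of permitted doses while still told to continue, with no instruction for that moment. Because the drug is taken at home, nobody is placed to settle the conflict dose by dose, and sites may advise patients differently. The next step refers back to the high-dose schedule, so its meaning depends on how the conflict is resolved.

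**Working it through.** **Inputs, all from 5.4.7.** Standard dosing: 4 mg, then 2 mg every 4 hours (the clock-based alternative). Step-up after 12 hours. High dose: 2 mg every 2 hours or 4 mg every 4 hours. Limit: 16 mg, also given as 8 capsules or tablets, in 24 hours.

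**1. The limit agrees with itself and with standard dosing.** 16 mg ÷ 8 = 2 mg per unit, which is the size of the standard repeat dose. Standard dosing by the clock gives 4 + 5 × 2 = 14 mg in the first 24 hours and 6 × 2 = 12 mg in each later 24 hours. Both are under 16 mg, so the conflict lies only with the high-dose step.

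**2. A full 24 hours at high dose.** Total = (24 ÷ interval) × dose.

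- 2 mg every 2 hours: 12 × 2 = 24 mg
- 4 mg every 4 hours: 6 × 4 = 24 mg

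Excess: 24 − 16 = 8 mg, and 8 ÷ 16 = 50%.

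**3. The sequence a patient would follow.** Standard doses at hours 0, 4 and 8 give 4 + 2 + 2 = 8 mg. Stepping up at hour 12, the cumulative totals are:

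| Hour from first dose | 2 mg every 2 h | 4 mg every 4 h |
|---|---|---|
| 12 | 10 mg | 12 mg |
| 14 | 12 mg | – |
| 16 | 14 mg | 16 mg (limit reached) |
| 18 | 16 mg (limit reached) | – |
| 20 | 18 mg (exceeded) | 20 mg (exceeded) |
| 22 | 20 mg | – |

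Reaching 16 mg is permitted. The first dose over the limit is due at hour 20 on either option, 8 hours after the step-up. The first 24 hours total 20 mg either way.

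**4. High dose alone.** If the earlier 8 mg is ignored, 16 mg is reached 14 hours (2 mg option) or 12 hours (4 mg option) after the first high dose. The dose due at hour 16 then takes the total to 18 mg or 20 mg. Leaving out the standard phase therefore does not remove the conflict.

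**5. The next step under each reading of its 24 hours.**

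- *Time on the high-dose schedule.* This takes 24 mg, so it cannot be completed within 16 mg.
- *Duration of the diarrhea.* A patient who stops at 16 mg can still meet it, so the step is reachable. A patient who instead followed the schedule through those 24 hours (12 hours standard, 12 hours high dose) would have taken 20 mg.

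The trigger fails under the first reading only. The schedule exceeds the limit under both.

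**The case against.** The strongest reply is that the note is simply a cap. The step-up is optional, the prohibition is emphatic and sits directly beneath it, and a rate followed by a maximum can be read as an instruction to dose at that interval until 16 mg and then stop. On that reading compliance is possible, and the limit forbids a total, not the schedule itself. This has some force, but the text does not say it. It tells the patient to go on until symptoms have been absent for 12 hours, and it gives no direction for a patient who reaches 16 mg with diarrhea continuing.

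A reader might also infer that a patient who respects the limit can never qualify for the next step and is left without further care. The documents do not support that. The 24 hours can be read as the duration of the diarrhea. The step for uncontrolled or complicated diarrhea of any grade offers hospitalization, intravenous fluids and octreotide without a time condition. The high-dose bullet itself allows additional treatment under local practice, and section 5.4.3 allows general supportive care as needed.

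Nor does a link to dose reductions follow from the 72-hour exemption in section 6.1. That exemption concerns Grade 3 diarrhea, whereas this schedule is for Grade 1 or 2.

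**Conclusion.** Section 5.4.7 contradicts itself. Either high-dose option, continued for 24 hours, gives 24 mg against a limit of 16 mg, an excess of 8 mg or 50%. This follows from the section's own figures, taking the schedule as written. The sequence in which the limit is passed at hour 20 and the first 24 hours total 20 mg also assumes that standard doses are taken by the clock, that the step-up comes at hour 12, and that the 24 hours run from the first dose. Extra standard doses taken after unformed stools would bring the crossing forward. The wording of the next step is ambiguous; it is not shown to be unreachable.

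The number of patients affected cannot be derived. A reader might multiply the 50.4% diarrhea incidence for selumetinib in section 7.3.1 by 21 patients (0.504 × 21 = 10.6) and conclude that about half the trial is exposed. That is an all-grade figure from pooled selumetinib studies. The conflict arises only in patients who have not improved after 12 hours of standard loperamide, and the documents give no rate for them.

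This is a supportive-care inconsistency that bears on patient safety because dosing is at home. The primary endpoint and the sample size are unaffected.

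**What to change.** The sponsor's medical team should reconcile three statements in 5.4.7: the high-dose schedule, the 24-hour limit and the wording that triggers the next step. One patient should be able to follow all three together. The revised text should say what happens when the limit is reached while diarrhea continues, and whether the 24 hours in the next step count time on high-dose loperamide or time with diarrhea. Which figure changes is a medical decision, and no view is offered here.

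The result should be carried into any patient instructions. The documents contain no loperamide hand-out, so what patients are told cannot be checked from them. The cost is a wording change in one section and in any such instructions, with no added procedures, visits or patients.
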